Evaluating the Telehealth-Single-Session Consultation Service at the Krasner Psychological Center

[name], [name], [name], [name], [name], [name]

Hypotheses, Aims, and Analytic Plan
January 18, 2021

Study Aims and Hypotheses

The goals of the study will be as follows:

1. To assess whether levels of proximal clinically-relevant outcomes (e.g, hope; readiness for change) is improved immediately following completion of the SSC, both in adolescent and adult clients.
2. To examine the perceived acceptability, usefulness, and client satisfaction following participation in the telehealth-Single-Session Consultation (SSC) service at the Krasner Psychological Center (KPC) among waitlisted adolescent and adult clients (ages 13 and older).
3. To assess the demand for and feasibility of providing the telehealth-SSC service at the Krasner Psychological Center (i.e., documenting the proportion of clients who choose to participate in the service when it is offered; documenting the number of sessions successfully completed, rescheduled, and/or cancelled).
4. To assess whether levels of psychological symptoms (e.g. anxiety, depression) significantly improve from pre-SSC to two weeks following completion of the telehealth-SSC.
5. To assess for the quality of therapeutic alliance established between the client and clinician during the telehealth-SSC

Hypotheses associated with each of these aims will be as follows:

1. Clients' proximal clinically-relevant outcomes (e.g, hope, measured by the Beck Hopelessness Scale – 4 item version, and readiness for change, assessed by the three-item “Readiness for Change Ruler”), which are hypothesized to serve as mechanisms for intervention effects, will improve from immediately pre to immediately post telehealth-SSC.
2. Adolescent and adult clients will perceive the telehealth-SSC at the KPC as acceptable and useful in addressing their clinical needs, indexed by mean ratings of at least 3.0 out of 5 across the five items on the “Consultation Feedback Form”.
3. The telehealth-SSC will show feasibility as a model for service provision at the KPC (i.e., a majority [$>50\%$] of clients who are offered the telehealth-SSC service will elect to receive it, and most [$>75\%$] of clients who schedule a telehealth-SSC appointment will attend)

4. Clients' overall levels of depression (measured by PHQ-9) and anxiety (measured by GAD-7) will reduce two weeks after the telehealth-SSC, relative to symptoms immediately prior to the telehealth-SSC
5. Adolescent and adult clients will report a satisfactory level of therapeutic alliance, defined as a mean rating of 4 on the 12-item scale

Sample Size Justification

We are primarily interested in obtaining precise estimates of feasibility and acceptability outcomes; client satisfaction ratings; and changes in possible change mechanisms (hope, readiness for change) and mental health outcomes (levels of anxiety, depression), which will aid in the planning of a larger-scale efficacy trial. A minimum client sample size of 30 will allow us to be relatively precise in our conclusions regarding feasibility outcomes, as well as change in hope, anxiety, and depression scores from pre-to-post-intervention, based on guidelines for pilot study planning proposed by Joulius (2005) and Whitehead et al (2016).

Analytic Plan

To address Hypothesis 1, we will conduct two 2-tailed paired samples t-tests to assess whether participants scores on the Beck Hopelessness Scale – 4 item version and the readiness change ruler significantly reduced from pre-SSC to post-SSC. A pre-post difference with a p-value of < .05 will indicate a significant change in hope from pre-SSC to post-SSC.

To address Hypothesis 2, we will examine mean scores on the “Consultation Feedback Form,” which contains 5 items rated on a 1-5 Likert scale by participants (e.g., “Did you find the consultation helpful in addressing your concern(s)?”; “How motivated do you feel to use your action plan?”) A mean score of 3.0 out of 5 or higher across participants in this study would indicate participants found the telehealth-SSC more than somewhat helpful in addressing their concerns.

To address Hypothesis 3, we will first divide the number of people who accepted the KPC’s invitation to take part in the telehealth-SSC service (whether or not they subsequently attend their scheduled session) by the number of people who declined the invitation to take part in the telehealth-SSC service. We will then divide the number of people who attended their scheduled telehealth-SSC session by the total number of people who scheduled an telehealth-SSC session, regardless of future attendance. If the first number exceeds .5 (50%), and the second number exceeds .75 (75%), we will conclude the SSC’s feasibility as a service delivery model.

To address Hypothesis 4, we will again use a 2-tailed paired samples t-test to assess whether participants’ GAD-7 and PHQ-9 score significantly reduced from pre-SSC to 2-week follow-up. A pre to follow-up difference with a p-value of < .05 will indicate a significant change.

To address Hypothesis 5, we will examine the mean scores on the Working Alliance Inventory (WAI), which contains 12 items rated on a 1-7 Likert scale by participants. A mean score of 4 (out of 7) or higher would represent a basic agreement between the SSC clinician and the client

on the tasks and goals of therapy as well as the existence of a quality therapeutic alliance. Thus, a mean score of 4 across participants in this study would indicate that the working alliance established in the telehealth-SSC is satisfactory.

We will use maximum likelihood estimation to address any item- and subject-level missing data that may emerge.

The false discovery rate (FDR) will be applied to identify potential false-positive results. Q-values will be computed for p-values from t tests using an online calculator applying Benjamini and Hochberg's (1995) approach (<https://www.sdmproject.com/utilities/?show=FDR>). Results will be considered significant if FDR corrected $q < 0.05$ (incurring maximum 5% false-positive rate amongst all tests meeting significance at $p < 0.05$). Both p and q values will be reported.

Study Timeline

Recruitment is projected to begin in approximately February 2021 and extend through approximately July 2021, but precise dates of study duration are difficult to predict with certainty, as they will depend on patient flow and waitlist length at the clinic where the trial is being conducted. Results are projected to be available for hypotheses 1-4 by September 2021.

References

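### Hypothesis 3 divides acceptors by decliners instead of by clients offered, so its 50% acceptance cut-off works as one third; confidence intervals would also serve the SAP's stated interest in precision

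*SAP*

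**What the plan says.** **Acceptance.** In Study Aims and Hypotheses, Aim 3 is to document what proportion of clients take up the service when it is offered. Hypothesis 3 sets the bar at a majority (>50%) "of clients who are offered the telehealth-SSC service will elect to receive it". In the Analytic Plan, the first Hypothesis 3 figure is the number accepting the invitation divided "by the number of people who declined the invitation to take part in the telehealth-SSC service". The second is the number attending divided by the number scheduled. Feasibility is concluded when both conditions are met; the rule, cut here just before its last percent sign, is "If the first number exceeds .5 (50%), and the second number exceeds .75 (75".

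**Precision.** The Sample Size Justification states: "We are primarily interested in obtaining precise estimates of feasibility and acceptability outcomes", along with satisfaction ratings and changes in mechanisms and symptoms, to help plan a larger efficacy trial. It then says "A minimum client sample size of 30 will allow us to be relatively precise in our conclusions regarding feasibility outcomes" and extends this to change in hope, anxiety and depression, "based on guidelines for pilot study planning". It gives no margin, SD, expected rate or confidence level.

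**Planned output.** Hypotheses 1 and 4 are judged by paired t-tests; for Hypothesis 4, "A pre to follow-up difference with a p-value of < .05 will indicate a significant change". Hypothesis 2 is judged by "A mean score of 3.0 out of 5 or higher across participants in this study", and Hypothesis 5 by a mean of 4 out of 7. For the t-tests the SAP commits to p-values and q-values. It names no confidence interval or standard error.

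**The concern.** The two parts of the SAP define different quantities and apply the same number to both. Accepted over offered is a proportion, for which 0.5 is a majority. Accepted over declined is an odds, for which a majority corresponds to 1.0. An analyst who follows the Analytic Plan literally would test a much weaker condition than the hypothesis states, and could report majority uptake when a majority did not take up the service. Anyone planning the larger trial from this figure would then misjudge how many clients need to be approached.

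Separately, a study whose declared interest is precise estimation would be expected to show how precise its estimates are. The plan as written does not require that.

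**Working it through.** **1. What the acceptance rule requires.** Inputs: the cut-off of .5 and the two denominators, from Hypothesis 3 and the Analytic Plan. Let *a* accept, *d* decline and *s* not respond, so that *a* + *d* + *s* are offered.

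- Analytic Plan: *a*/*d* > 0.5. If *s* = 0, then *d* = *n* − *a*, and *a*/(*n* − *a*) > 0.5 is the same as *a*/*n* > 0.5/1.5 = 1/3.
- Hypothesis 3: *a*/(*a* + *d* + *s*) > 0.5. If *s* = 0, this is the same as *a*/*d* > 1.0.

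The counts below are illustrations; the SAP gives none.

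| Accept | Decline | Silent | *a*/*d* | Rule in Analytic Plan | Share of offered | Hypothesis 3 |
|---|---|---|---|---|---|---|
| 10 | 20 | 0 | 0.50 | fails | 33.3% | fails |
| 11 | 19 | 0 | 0.58 | passes | 36.7% | fails |
| 16 | 14 | 0 | 1.14 | passes | 53.3% | passes |
| 34 | 66 | 0 | 0.515 | passes | 34.0% | fails |
| 20 | 30 | 50 | 0.67 | passes | 20.0% | fails |

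With 30 offered and all answering, the lowest passing count is 11 under the Analytic Plan and 16 under Hypothesis 3.

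**2. How often this matters.** Assume true acceptance of 40% and that everyone answers. Exact binomial probabilities of meeting the acceptance criterion are:

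- 30 offered (assumed): P(*a* ≥ 11) = 0.709 under the Analytic Plan, against P(*a* ≥ 16) = 0.097 under Hypothesis 3.
- 100 offered (assumed): P(*a* ≥ 34) = 0.909, against P(*a* ≥ 51) = 0.017.

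**3. Precision at 30.** The SAP gives no inputs from which 30 could be reproduced, so the check is what 30 delivers. A 95% level is assumed.

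- Proportion at 50%: 1.96 × √(0.25/30) = 0.179.
- Proportion at 75%: 1.96 × √(0.1875/30) = 0.155.
- Mean or mean change: t(0.975, 29)/√30 = 0.373 SD.

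Examples with Wilson intervals: attendance of 23/30 = 76.7% has an interval of 59% to 88%, and acceptance of 16/30 = 53.3% has 36% to 70%.

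The SAP does not say whether 30 counts clients offered, scheduled, attending or followed up. If 30 attend, the lowest passing attendance is 30/39 = 76.9% (62% to 87%), because 30/40 = 0.75 does not exceed the cut-off. If 30 accept, the lowest pass on Hypothesis 3's definition is 30/59 = 50.8% (38% to 63%).

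**The case against.** **The denominator is only a slip.** The (50%) label in the decision rule suggests that a proportion was meant, and the attendance ratio in the same paragraph has the right denominator. That is probably so. But the calculation is spelled out step by step, and an analyst who follows it obtains an odds.

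**The acceptance figure alone decides nothing.** This stands. Attendance must exceed 75% as well, so the error leads to a wrong feasibility conclusion only when attendance passes.

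**One third is not a fixed floor.** This also stands. It assumes that everyone offered gives an answer. Silence drops out of the plan's ratio altogether, so the share of those offered can fall below one third. The caveat makes the problem larger.

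**The missing intervals are mainly a reporting omission.** Largely fair. The SAP does not rule out SDs or intervals. Hypothesis 3 intervals can be computed from reported counts, and Hypothesis 1 and 4 intervals can be recovered from the mean change, n and exact p-value. The Hypothesis 2 and 5 means have no planned test, so they would need an SD. The sample size also rests on two cited guidelines whose content cannot be checked here.

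**Stronger readings to avoid.** A reader might infer that 30 is too few, or that a result such as 23/30 should fail because its lower limit lies below 75%. The SAP supports neither. It sets no precision target that 30 misses, and its cut-offs are point-estimate criteria, which are legitimate in a pilot.

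**Conclusion.** The denominator is wrong as written: the Analytic Plan contradicts Aim 3 and Hypothesis 3. The stated majority becomes anything above one third when all clients offered respond, and possibly less when some do not. Under the assumptions of 40% true acceptance and full response, the chance of meeting the criterion rises from about 0.10 to 0.71 with 30 offered, and from about 0.02 to 0.91 with 100. These sizes depend on assumed numbers offered; the contradiction itself does not. It should be corrected before the acceptance figure is computed.

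The precision point is separate and secondary. It is a cheap improvement that follows from the SAP's own statement of interest, and it is no evidence against the sample size. The half-widths of about 18 points, 15.5 points and 0.37 SD hold for a denominator of 30 and narrow if more clients are offered the service or scheduled.

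**What to change.** 1. In the Analytic Plan for Hypothesis 3, compute acceptance as clients accepting divided by all clients offered the service, keeping non-responders in the denominator. Apply the >50% cut-off to that figure. Leave the attendance ratio and its cut-off as they are.
2. Report 95% confidence intervals for the two Hypothesis 3 proportions (Wilson or exact), the Hypothesis 2 and 5 means, and the Hypothesis 1 and 4 mean changes (t-based), beside the planned p-values, q-values and cut-offs. The cut-offs stay as point-estimate criteria.
3. In the Sample Size Justification, state the expected 95% half-widths and say which clients the 30 counts. The guideline citations can stay.

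The cost is a few sentences and routine output. No extra clients are needed, and no extra data beyond a count of everyone offered the service, which Aim 3 already requires. The downsides are small: the acceptance rule becomes harder to pass, and results near a cut-off will visibly be uncertain.

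### Does describing the readiness ruler as tested for a reduction put the Hypothesis 1 analysis at odds with its hypothesis?

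*SAP*

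**What the plan says.** Aim 1 of the SAP reads: "To assess whether levels of proximal clinically-relevant outcomes (e.g, hope; readiness for change) is improved immediately following completion of the SSC". Hypothesis 1 names the two measures, the four-item Beck Hopelessness Scale for hope and a three-item ruler for readiness, and says that these outcomes "will improve from immediately pre to immediately post telehealth-SSC".

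The Hypothesis 1 paragraph of the Analytic Plan sets two two-sided paired t-tests. They are to show whether scores on the hopelessness scale and "the readiness change ruler significantly reduced from pre-SSC to post-SSC". The next sentence gives the decision rule: a pre-post difference with p below .05 "will indicate a significant change in hope from pre-SSC to post-SSC". Readiness is not named there.

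Near the end of the Analytic Plan, q-values are to be computed for the p-values from the t-tests. "Results will be considered significant if FDR corrected" q is below 0.05. The SAP gives no range, anchors or scoring direction for the ruler.

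**The concern.** A single verb of reduction governs two scales whose names point opposite ways. Less hopelessness is a gain; less readiness is, on the natural reading, a loss. Taken literally, the analysis would look for the opposite of what Hypothesis 1 predicts for readiness. The decision sentence does not put this right, because it mentions only hope.

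The plan's other pair of t-tests shows no such mismatch. Hypothesis 4 says that depression and anxiety "will reduce two weeks after the telehealth-SSC", and its analysis asks whether the "GAD-7 and PHQ-9 score significantly reduced from pre-SSC to 2-week follow-up". Readiness is therefore the only one of the four t-test outcomes whose analysis wording seems to run against its hypothesis.

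The point at stake is interpretation. A two-sided test rejects in either direction, so the sign of the mean change is what separates improvement from worsening. Readiness is also named as a possible mechanism, and its estimated change is meant to inform a larger trial. If the supporting sign were truly in doubt, a significant result could be read either way.

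**Working it through.** The SAP gives no effect size, SD or power for this test, so there is no figure of its own to reproduce. The check has two parts.

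**1. The texts side by side**

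| Place in the SAP | What it fixes for readiness |
|---|---|
| Aim 1; Hypothesis 1 | The construct should improve |
| Analytic Plan, Hypothesis 1, description of the tests | The score is said to be reduced |
| Analytic Plan, Hypothesis 1, decision sentence | A difference at p < .05; no sign; names hope only |
| Analytic Plan, false discovery rate paragraph | q < 0.05 for all t-tests; no sign |

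The first row concerns the construct and the second the score. They conflict only if a higher ruler score means more ready. That is plausible from the scale's name but is an assumption here. If the ruler is scored the other way, there is no slip at all. Neither rule that decides significance requires a reduction.

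**2. Does the verb alter any result?**

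Inputs: n = 30 (the minimum in Sample Size Justification), two-sided alpha 0.05, and four t-tests (hopelessness, ruler, PHQ-9, GAD-7). I assume 30 complete pairs and, for illustration, a mean change of 0.5 SD of the paired differences.

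- Test statistic: t = d × √n = ±0.5 × √30 = ±2.74 on 29 degrees of freedom.
- Two-sided p = 0.0104 for either sign.
- Benjamini-Hochberg with four tests: q is at most 4 × 0.0104 = 0.042, whatever the other three p-values.
- Smallest observed change reaching p < .05: 2.045 / √30 = 0.373 SD, the same in both directions.

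Replacing the verb of reduction with one of increase leaves p, q, the threshold and the estimated mean change as they were.

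**If a reduction were the criterion**

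Suppose the plan did require a significant fall, and readiness truly rises.

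| True rise (assumed, SD of change) | Chance of a significant rise | Chance of a significant fall |
|---|---|---|
| 0.3 | 35.5% | 0.02% |
| 0.5 | 75.4% | below 0.001% |
| 0.8 | 98.9% | below 0.001% |

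Such a rule would almost never be met when the service works as hoped. But it is not the plan's rule: the decision sentence asks for a difference, without a sign. The last column shows what a literal misreading would cost and does not describe the planned analysis.

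**The case for a change.** The strongest argument for a change is that a prespecified analysis should not leave the supporting sign to inference. Significance says nothing about direction in a two-sided test, so direction has to come from the text, and here the text of the analysis points the wrong way for a named mechanism. The decision sentence leaves readiness out, the false discovery rate paragraph supplies no sign, and the repair would take about two sentences. Leaving scoring details to a protocol is no answer, since the complaint rests on words the SAP does contain.

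Part of this stands. The verb is wrong for the ruler if higher scores mean more ready, and the decision sentence would be tidier if it named both outcomes.

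The rest does not. Direction does come from the text: the Hypothesis 1 paragraph announces that it addresses Hypothesis 1, and that hypothesis says improvement. An analyst who knows the ruler's scoring is unlikely to report a fall in readiness as support for a prediction that readiness will improve. Nor is readiness left without a significance criterion, because the q < 0.05 rule applies to the p-values of all the t-tests, including the ruler's.

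**Conclusion.** The concern identifies a probable clerical slip and does not call for a change to the plan. One verb, correct for hopelessness, was extended to a scale on which improvement probably means a higher score. It touches one of the two Hypothesis 1 tests, or one of four t-tests overall, and only in how that test is described.

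The test, its p-value and q-value, the estimate and the sample size are the same under either wording, and Hypothesis 1 settles which direction counts as support. Rewording would make the document neater without changing a result or a sensible conclusion.

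That the verb is a slip at all assumes that higher ruler scores mean more ready, which the SAP does not state. The decision to leave the plan alone holds under either scoring. The 0.5 SD example and the assumed true rises are illustrations only; the equality of p for the two signs holds for any size of change.

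### The Hypothesis 3 uptake rule divides acceptors by decliners, so its .5 cut-off is passed just above 33.3% uptake instead of the stated majority

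*SAP*

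**What the plan says.** The SAP defines uptake in two places as a share of clients offered the service. Under Study Aims and Hypotheses, Aim 3 speaks of "documenting the proportion of clients who choose to participate in the service when it is offered". Hypothesis 3 sets the benchmark at a majority, above 50%, "of clients who are offered the telehealth-SSC service will elect to receive it".

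The Analytic Plan then gives the formula for Hypothesis 3. The numerator is everyone who accepted the "invitation to take part in the telehealth-SSC service (whether or not they subsequently attend their scheduled session"). That count is divided "by the number of people who declined the invitation to take part in the telehealth-SSC service". A second ratio covers attendance: those who attended, divided "by the total number of people who scheduled an telehealth-SSC session, regardless of future attendance". The decision rule follows: "If the first number exceeds .5 (50%), and the second number exceeds .75 (75%), we will conclude the" service model feasible.

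**The concern.** The quantity computed is not the quantity hypothesised. Accepted over declined is an odds. It has no upper limit of 1 and cannot be read as a percentage: at 60% uptake it equals 1.5. The cut-off of .5 belongs to a proportion, and applied to an odds it sets a much lower bar.

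The uptake ratio is one of only two numbers that decide whether the service is called feasible. The Sample Size Justification names feasibility among the study's primary interests and says the estimates will help plan a larger efficacy trial. Followed literally, the rule can report that the uptake benchmark was met when nearly two thirds of clients declined.

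The denominators also differ in coverage. Hypothesis 3 counts everyone offered, whereas the formula counts only those who accepted or declined. The SAP does not say where a client who never replies belongs.

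**Working it through.** **Inputs from the SAP.** Hypothesis 3 threshold: more than 50% of clients offered. Analytic Plan formula: accepted (A) divided by declined (D), to exceed .5. Minimum client sample: 30 (Sample Size Justification). The number offered the service is not stated, so it is assumed below over a range of 30 to 90.

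**Step 1: can the stated 50% be reproduced from the written formula?** Suppose every client offered either accepts or declines, and let p = A/(A + D). Then A/D = p/(1 − p).

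- Written rule: p/(1 − p) > 0.5, so p > 0.5 − 0.5p, so 1.5p > 0.5, so p > 1/3 = 33.3%.
- At p = 50% the written ratio is 0.5/0.5 = 1.0, not 0.5.
- The rule A/(A + D) > 0.5 gives p > 50%, as in Hypothesis 3. On the odds scale the equivalent cut-off would be A/D > 1.0.

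The written formula therefore does not reproduce the stated threshold. This step needs no assumption about sample size. The inequality is strict, so exactly one third fails and anything above it passes.

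**Step 2: a single example.** With 100 offered, 40 accepting and 60 declining, the written ratio is 40/60 = 0.67 and passes. The proportion is 40/100 = 0.40 and fails.

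**Step 3: chance of passing the uptake component.** Exact binomial probabilities, with all clients answering:

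| Clients offered (assumed) | Acceptors needed, written rule | Acceptors needed, majority rule | True uptake 35%: written / majority | True uptake 40%: written / majority |
|---|---|---|---|---|
| 30 | 11 | 16 | 0.49 / 0.03 | 0.71 / 0.10 |
| 60 | 21 | 31 | 0.55 / 0.006 | 0.82 / 0.04 |
| 90 | 31 | 46 | 0.58 / 0.001 | 0.88 / 0.02 |

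For instance, with 60 offered, 20/40 = 0.50 does not exceed .5, but 21/39 = 0.54 does. So 21 acceptors (35%) suffice, against 31 for a majority.

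**Step 4: clients who do not reply.** Take a hypothetical 100 offered, with 20 accepting, 30 declining and 50 silent. True uptake is 20/100 = 20%.

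- Silent clients left out of both counts: 20/30 = 0.67, which passes.
- Silent clients counted as declining: 20/(30 + 50) = 0.25, which fails.

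Under the written formula the verdict depends on a coding rule that the SAP does not state. With all clients offered in the denominator, the result is 20% under either coding.

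**The case against.** The strongest reply is that this is a drafting slip with recoverable intent. Aim 3 says proportion, Hypothesis 3 says majority, the cut-off is labelled as a percentage, and the attendance ratio in the same paragraph has a proper total as its denominator. A sensible analyst might compute the proportion anyway. That is probably what was meant, but the sentence is an explicit, pre-stated formula and nothing else in the SAP overrides it. The percentage label shows that the cut-off was chosen for a different quantity from the one computed.

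Three further points refine the finding:

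- **Joint rule.** Feasibility also requires attendance above 75%, so the error loosens one component and cannot by itself produce a feasibility conclusion. This stands. Attendance, however, is measured only among clients who scheduled a session and says nothing about how many declined. Once attendance is met, the faulty ratio alone decides.
- **Assumed number offered.** The probabilities in Step 3 are illustrative and cover the uptake component only. This stands too, but the direction is the same across 30 to 90, and the 33.3% threshold does not depend on the number.
- **Non-response.** The SAP mentions no non-responders, and a protocol not at hand may define how they are coded. The non-response effect is therefore conditional, and Step 4 shows that it can go either way.

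The error does not touch the t-tests for Hypotheses 1 and 4.

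**Conclusion.** The uptake rule is wrong as written. Its effective threshold is just above 33.3% of clients who accept or decline, against the more than 50% of clients offered in Hypothesis 3. When all clients answer, the formula and the hypothesis give opposite answers on uptake for any observed value above 33.3% and up to 50%. That result is algebra and rests on no outside figure.

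The practical size depends on an assumed 30 to 90 clients offered, all answering: at a true uptake of 40%, the component passes with probability 0.71 to 0.88 as written, against 0.10 to 0.02 under the hypothesis. Because this is a pre-stated decision threshold that can reverse the uptake conclusion, it should be corrected before the feasibility result is read.

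**What to change.** In the Analytic Plan for Hypothesis 3, replace the first ratio with wording such as: the number of clients who accepted the invitation, divided by the total number of clients offered the service (accepted, declined and no response), to be compared with .50. Count clients, not invitations, so that someone invited twice enters once. Leave the attendance ratio and its .75 cut-off as they are.

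The cost is one sentence of SAP text and a record of how many clients were offered the service, which the proportion in Aim 3 already requires. The benchmark becomes harder to meet than under the present formula: 16 instead of 11 acceptors of 30 offered, or 31 instead of 21 of 60. That is the level Hypothesis 3 already sets.

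### The SAP promises maximum likelihood for clients with a missing score, but the paired t-tests named for all four change outcomes cannot use such clients

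*SAP*

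**What the plan says.** All the relevant statements are in the SAP's Analytic Plan, apart from the purpose and sample size, which are under Sample Size Justification.

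- **Hypothesis 1** (hopelessness and readiness, immediately before and after the session): "we will conduct two 2-tailed paired samples t-tests".
- **Hypothesis 4** (PHQ-9 and GAD-7, before the session and two weeks after): "we will again use a 2-tailed paired samples t-test", to see whether "GAD-7 and PHQ-9 score significantly reduced from pre-SSC to 2-week follow-up".
- **Missing data**, in one sentence after the hypothesis-specific methods: "We will use maximum likelihood estimation to address any item- and subject-level missing data that may emerge". It names no model and no link to the tests.
- **Multiplicity**: "Q-values will be computed for p-values from t tests using an online calculator".
- **Size and purpose**: "A minimum client sample size of 30 will allow us to be relatively precise", and the change estimates are among the results "which will aid in the planning of a larger-scale efficacy trial". No loss to follow-up is assumed or allowed for.

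**The concern.** A paired t-test is a one-sample test on within-client differences. A client with one score has no difference, so the test as named leaves that client out. The missing-data sentence says such clients will be handled by maximum likelihood. The SAP does not say which statement gives way, and three readings are open:

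1. The mean change is estimated directly by maximum likelihood from all available scores. This is sound, but it is not the named test.
2. Incomplete pairs are dropped. This is valid if loss is completely random and biased if loss depends on the pre-session score. The maximum likelihood sentence then goes unused.
3. Each missing score is filled once with its likelihood-based prediction and the t-test treats it as observed. The standard error is then too small.

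At stake are the PHQ-9 and GAD-7 change estimates, which are meant to inform a larger trial, and their p and q values. With no rule fixed, the choice could be made after the data are seen. Hypothesis 1 is less exposed because both scores are taken around one session. Item-level gaps, and the mean ratings for Hypotheses 2 and 5, are not part of this point.

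**Working it through.** **Inputs from the SAP:** at least 30 clients, two-sided paired t-tests, p < .05 per test, then q < .05. The figure of 30 rests on cited pilot guidelines, with no effect size, SD or loss rate, so it cannot be re-derived. It is not disputed here.

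**Assumptions (not in the SAP):** bivariate normal scores with SD 1, no true change, pre-session score always observed, correlation r between pre and follow-up of 0.3, 0.6 or 0.8, and the loss rates and mechanisms below. Error rates come from 100,000 simulated trials per cell (Monte Carlo SE about 0.07 percentage points) and are per test at .05.

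**Reading 2, dropped pairs**

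Under random loss of 5 to 30% (r=0.6) the error is 4.9 to 5.0%, so there is no problem.

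If loss depends on the pre-session score x, the bias in mean change is −(1 − r) × (mean of x among those retained). With logit(loss) = −1.35 + 1.0x, 24.4% are lost and the mean of x among those retained is −0.209 SD. The bias is therefore:

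- r=0.3: 0.7 × 0.209 = 0.146 SD
- r=0.6: 0.4 × 0.209 = 0.084 SD
- r=0.8: 0.2 × 0.209 = 0.042 SD

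The simulated biases agree. The bias runs toward worsening if higher-symptom clients are lost and toward improvement if lower-symptom clients are lost. Simulated results, averaged over the two directions:

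| Scenario | Bias in SD, r=0.8 / 0.6 / 0.3 | Error, r=0.8 / 0.6 / 0.3 |
|---|---|---|
| (a) slope 1.0 (odds ratio 2.7 per SD), 24% lost | 0.04 / 0.08 / 0.15 | 6.1 / 7.2 / 8.8% |
| (b) slope 1.0, 10% lost | 0.02 / 0.04 / 0.06 | 5.1 / 5.5 / 5.8% |
| (c) slope 0.5 (odds ratio exp(0.5) = 1.65), 22% lost | 0.02 / 0.04 / 0.07 | 5.3 / 5.6 / 6.0% |

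**Reading 3, fill once and then t-test (random loss)**

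| Loss | Error at r=0.6 | Range, r=0.3 to 0.8 |
|---|---|---|
| 5% | 5.9% | 5.9–6.2% |
| 10% | 7.4% | 6.9–7.5% |
| 20% | 10.5% | 9.4–11.3% |
| 30% | 14.7% | 12.6–16.0% |

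The cause can be checked by hand at r=0.6 and 20% loss. The change has regression part (1 − 0.6)² = 0.16 and residual variance 1 − 0.6² = 0.64. Filled scores carry no residual, so the t-test sees a variance of about 0.16 + 0.8 × 0.64 = 0.672 and reports an SE of about √(0.672/30) = 0.150. The correct large-sample value is √(0.64/24 + 0.16/30) = 0.179. The simulation gave 0.148 reported against 0.180 true.

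**Reading 1, likelihood estimate of the change**

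When only follow-up scores are missing, this has a closed form. Here c marks complete pairs, b is the slope of follow-up on pre score in those pairs, s² is the residual variance, s₁₁ is the variance of x, and SSx_c is the sum of squares of x in complete pairs:

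- change = mean(y_c) + b[mean(x) − mean(x_c)] − mean(x)
- variance = s²/n_c + (b − 1)² s₁₁/n, on n_c − 1 degrees of freedom
- the small-sample version adds s²[mean(x) − mean(x_c)]²/SSx_c

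With no loss this is algebraically the paired t-test. Across all scenarios the bias was at most 0.0014 SD. The error was 4.9 to 5.8% with the plain REML standard error and 4.8 to 5.1% with the small-sample one.

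The small-sample method has to be named. Maximum likelihood with a large-sample z test gives 6.3 to 7.1% error with loss. With none it gives 2 × P(t₂₉ > 1.96 × √(29/30)) = 6.4%.

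**The case against.** The strongest reply is that the plan is under-specified, not contradictory: paired t-tests by default, with maximum likelihood stepping in if scores are missing. Since the likelihood model reduces to the paired t-test with complete data, reading 1 may be what was meant. That is fair, and a short linking statement would settle it. As written, though, no such model is named, and the small-sample method, which affects the error rate, is left open.

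Several other points stand as limits on size:

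- The largest error rates belong to reading 3, and the SAP mentions no imputation. They show a possible misuse, not the plan.
- Without reading 3 the effect is modest unless loss is both substantial and strongly tied to the pre-session score.
- The SAP's final criterion is q < .05. With four independent null tests and loss only in PHQ-9 and GAD-7, the chance of any false q < .05 with dropped pairs is 5.1 to 5.6% in scenarios (b) and (c). In scenario (a) it is 5.7, 6.4 and 7.9% at r=0.8, 0.6 and 0.3.
- This is a pilot concerned mainly with estimation. That lowers the weight of type I error, but bias in the estimated change still matters.
- A mixed model's time effect is also tested with a t statistic, so the false discovery rate sentence needs only a clarifying change.
- The likelihood model removes bias only when loss depends on observed scores. Loss depending on the unseen follow-up score was not examined, and no method named here would cure it.

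**Conclusion.** The concern holds. The SAP commits to maximum likelihood for missing clients and to a test that cannot use them, without joining the two. The practical exposure is Hypothesis 4.

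If the t-tests are run on complete pairs, the consequence ranges from none (random loss) through small (scenarios b and c) to moderate (scenario a). If missing scores are filled once and tested as observed, the p and q values are clearly too small. These sizes rest on assumed loss rates, mechanisms and correlations at the minimum sample of 30. With no subject-level loss, nothing changes. The point should be corrected because the repair is nearly free; it does not threaten the study as a whole.

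**What to change.** 1. For PHQ-9 and GAD-7, and for the Hypothesis 1 outcomes if any post-session score is missing, take the p and q values from the time effect of a likelihood-based model of both time points, using every client with at least one score. One suitable form is a mixed model with unstructured 2×2 covariance, fitted by REML, with a Kenward-Roger type standard error and degrees of freedom.
2. Reword the false discovery rate sentence so that its p-values come from the four change tests.
3. Keep the complete-pair t-test as a sensitivity analysis and report the number of complete pairs for each outcome.
4. State that singly filled scores will not be t-tested as if observed.

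The cost is a few sentences in the SAP and a few lines of standard software, with a slightly less simple description. Almost no precision is gained: at 20% random loss and r=0.6 the true SE is 0.180 SD against 0.183 SD for complete pairs. The gain is freedom from bias when loss depends on the pre-session score, and an error rate close to 5%.

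A lighter option is to state that the t-tests use complete pairs only and to report their number. This removes the inconsistency but leaves the bias.
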